4.3 Follow-Up Visit Windows

Follow-up visits will be scheduled at appointed times after the date of treatment. Follow-up visits should be scheduled within the ideal window when possible; however, any available data collected in the analysis windows will be summarized as occurring within the given window. Thus, a period during which each visit is allowed, i.e. window, is provided in **Table 3** (Zone 2) and **Table 4** (Zone 0/1).

Follow-up Visit	Ideal Window (days)	Analysis Window (days)	Adverse Event Absolute Analysis Window (days)
Procedure	0	0	0
Post-Procedure	1-14	1-14	-
1 Month	23-44	15-59	1-30
6 Months	150-210	60-242	31-182
12 Months	275-455	243-546	183-365
24 Months	640-820	547-911	366-731
36 Months	1005-1185	912-1275	732-1096
48 Months	1370-1550	1276-1640	1097-1461
60 Months	1735-1915	1641-2006	1462-1826

Table 3: Zone 2 Cohorts Schedule of Follow-up Visits and Time Periods

		· ·	
Follow-up Visit	Ideal Window (days)	Analysis Window (days)	Adverse Event Absolute Analysis Window (days)
Phase 1 Procedure:	-7 up to -1 days before	-60 up to -1 days	-60 up to -1 days
Great Vessel	Phase 2 Procedure	before Phase 2	before Phase 2
Revascularization		Procedure	Procedure
Phase 1 Evaluation	-6 up to 0 days before Phase	-59 up to 0 days	-59 up to 0 days
	2 Procedure*	before Phase 2	before Phase 2
		Procedure*	Procedure*
Phase 2 Procedure:	0	0	0
Index Endovascular			
Procedure			
Post Procedure	1-14	1-14	-
1 Month	23-44	15-59	1-30
6 Months	150-210	60-242	31-182
12 Months	275-455	243-546	183-365
24 Months	640-820	547-911	366-731
36 Months	1005-1185	912-1275	732-1096
48 Months	1370-1550	1276-1640	1097-1461
60 Months	1735-1915	1641-2006	1462-1826

Table 4: Zone 0/1 Cohorts Schedule of Follow-up Visits and Time Periods

* Although Phase 1 Evaluation can occur on the same day as the Index Endovascular Procedure, the Phase 1 Evaluation must occur before the Index Endovascular Procedure

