Expected Time to Complete Enrollment	
 • Zone 2 - Aortic Aneurysm Subject accrual: 18-24 months • Zone 0/1 - Aortic Aneurysm Subject accrual: 48-60 months • Follow-up – Five years from treatment date Total study duration –Ten years
Schedule of Events Zone 2 Cohorts	
Screening Evaluation: (Within 30 days prior to enrollment unless otherwise noted)
 
 • Physical examination, medical history • Modified Rankin Scale • Spinal Cord Ischemia Scale • NIH Stroke Scale • Spiral Computed Tomographic Angiography (CTA) of the chest, abdomen, and pelvis (contrast only) within 90 days prior to enrollment • Serum creatinine concentration 
Procedure:
 
 • Endovascular repair with the TBE Device with distal extension using the Conformable GORE® TAG® Thoracic Endoprosthesis as needed • Post deployment angiogram

	
Post Procedure: (Performed prior to discharge unless otherwise noted)
 
 • Physical examination • Modified Rankin Scale • Spinal Cord Ischemia Scale • NIH Stroke Scale • In addition, NIH Stroke Scale should be performed for any Subject suspected of having a stroke event that undergoes the treating site's stroke Protocol during the study interval from the initiation of index endovascular procedure until discharge, and should be performed as soon as possible after learning of the event 
Follow-Up Evaluations: Intervals: 1, 6, 12, 24, 36, 48, and 60 months post-treatment
 
 • Physical examination • Modified Rankin Scale (also completed at 3 months for Subjects suspected of experiencing a stroke event through 30 days) • Spinal Cord Ischemia Scale • Spiral CTA of the chest (contrast) • NIH Stroke Scale (one month only) • Dissection Subjects only: Spiral CTA of the chest, abdomen, and pelvis (contrast) • Spiral CT of the chest (non-contrast - one month only, or if endoleak suspected) • Dissection Subjects only: Spiral CTA of the chest, abdomen, and pelvis (non-contrast - one month only, or if endoleak suspected)

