5.5.4 Adverse Events

Adverse events (AEs) will be summarized for main reporting efforts. Adverse events are defined as any untoward medical occurrences in a Subject whether device-related or not. All AEs will be recorded on the appropriate CRF and documented in the Subject's permanent medical record. The Investigator at each Site is ultimately responsible for reporting all AEs to the Sponsor, as well as to the IRB, as applicable.

Adverse events will be summarized by incidence (i.e. a specific AE will not be counted more than once for a Subject within each window) in each analysis time window using MedDRA coded terminology. Analysis time windows will begin with the initial endovascular treatment window for all cohorts; AEs with onset prior to endovascular treatment (Zone 0/1 cohorts only) will be summarized separately. The denominator for each window will be calculated as the number of Subjects remaining in follow-up as of the beginning of the analysis window. At a minimum, separate summaries by severity (serious, non-serious) will be prepared. If summaries are prepared by relationship, the following categories will be considered as related to device/procedure: related to device, related to device and endovascular procedure, or related to endovascular procedure.

Partial dates (month and/or day unknown) for AE onset and AE resolution dates will be allowed for AE analysis time window determination. Exact imputation logic will be documented in the appropriate specifications document. In general, partial dates will be imputed to be most conservative with regard to timing after initial endovascular procedure date.

Candidate AEs for Primary Endpoint and Success Outcomes will be reviewed by the independent CEC and adjudicated (outlined in Appendix A).

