5.5.4.1.3 Adverse Event Reporting and Coding

AEs will be reported on the appropriate CRF and documented in the Subject's permanent medical record. The Investigator at each Site is ultimately responsible for reporting AEs to the Sponsor.

The following information on each reported Adverse Event will be collected:

- Adverse Event Name •
- Adverse Event Onset Date •
- Relationship
- Classification (Serious or Non-Serious) •
- Treatment
- Outcome
- **Resolution Date**

Adverse Events will be coded using the Medical Dictionary for Regulatory Activities (MedDRA).

Adverse Event submission guidelines:

- Adverse Event reporting begins once the patient is enrolled in the study. All Adverse Events should be reported from enrollment through study completion / discontinuation.
- Provide a diagnosis if possible. If unable to provide a • diagnosis, report the symptoms as separate events. Adverse Events should be reported using the full name without abbreviations or narratives.
- Adverse Events with an outcome status of "Ongoing" • should be assessed at each follow-up evaluation to determine if the event has resolved. Adverse Events ongoing at study completion / discontinuation should be left as "Ongoing" on the AE case report form.

GORE CONFIDENTIAL INFORMATION

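### Adverse events with onset on days 1827-2006 are collected but have no AE analysis window, so the by-window AE tables would leave them out

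*SAP*

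**What the plan says.** SAP section 4.3 gives three sets of windows for each visit: ideal, analysis, and a third headed as the absolute analysis window for adverse events. The 60-month row is the same in Table 3 (Zone 2) and Table 4 (Zone 0/1): "60 Months 1735-1915 1641-2006 1462-1826". The row before it is "48 Months 1370-1550 1276-1640 1097-1461". On use of the visit windows, the section says that "any available data collected in the analysis windows will be summarized as occurring within the given window".

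Section 5.5.4.1.3 sets the collection period: "All Adverse Events should be reported from enrollment through study completion / discontinuation". Section 5.5.4 summarizes AEs by incidence "in each analysis time window using MedDRA coded terminology", and explains that "a specific AE will not be counted more than once for a Subject within each window". On dating it says: "Partial dates (month and/or day unknown) for AE onset and AE resolution dates will be allowed for AE analysis time window determination". It names no cumulative category and no category after day 1826.

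Section 5.5.7 also summarizes site-reported reinterventions by analysis time window, without naming the column, and adds a Kaplan-Meier analysis of time to the first one. The Protocol Summary gives follow-up as "Five years from treatment date".

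**The concern.** The collection rule and the tabulation rule do not end on the same day. AEs are recorded for as long as the subject is in the study, and a subject whose 60-month visit is on time may still be in the study on day 1915. One whose visit is late but usable may be there on day 2006. The AE windows stop at day 1826.

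At every earlier visit this does no harm, because an event dated past the end of one AE window falls into the next. The 60-month window has no successor.

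At stake is the reporting of late device safety. The 60-month contrast CTA is the last scheduled imaging. Section 5.5.5 summarizes Core Lab findings by applicable analysis window. If that means the analysis window column, a finding on day 1900 counts at 60 months, while an AE with onset that same day appears in no AE window. The two displays for one visit would then differ without explanation.

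**Working it through.** **Inputs, all from SAP Tables 3 and 4**
- 60 months: ideal 1735-1915, analysis 1641-2006, AE 1462-1826.
- 48 months: ideal 1370-1550, AE 1097-1461.
- AE windows in order: 0; 1-30; 31-182; 183-365; 366-731; 732-1096; 1097-1461; 1462-1826.

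**1. The plan's cut-off.** 60 × 365.25/12 = 1826.25, so day 1826 is five years. This reproduces the SAP's figure.

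**2. Coverage.** Each AE window starts the day after the previous one ends, so days 0-1826 are covered without gaps. Up to the end of the 60-month analysis window, the uncovered days are 1827-2006: 2006 − 1826 = 180 days. Of these, 1915 − 1826 = 89 lie inside the ideal window.

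**3. Share of allowed visit days after the cut-off.**
- Ideal: 89 / (1915 − 1735 + 1) = 89/181 = 49.2%.
- Analysis: 180 / (2006 − 1641 + 1) = 180/366 = 49.2%.

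These are shares of calendar days. They become shares of visits only under an assumed spread of visit days, which the documents do not give. Assuming normally distributed visit days with SD 20 to 45:

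| Mean visit day | Proportion of visits after day 1826 |
|---|---|
| 1810 | 0.205 to 0.357 |
| 1825 (ideal midpoint) | 0.470 to 0.487 |
| 1840 | 0.618 to 0.750 |

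**4. Share of AEs found at the final visit.** This depends on how onset is dated.
- *Onset dated to the visit* (as may happen with an imaging finding): the share equals the share of late visits, about half if visits are spread evenly or centred on day 1825.
- *Onset uniform between day 1460 (48-month ideal midpoint) and the final visit on day V*: the share with onset after the cut-off is max(0, V − 1826) / (V − 1460). Averaged over V = 1735 to 1915 it is 5.2%; over V = 1641 to 2006 it is 9.2%. For the latest allowed visits it is 89/455 = 19.6% (V = 1915) and 180/546 = 33.0% (V = 2006).

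**5. Is the rate for days 1462-1826 biased?** Suppose AEs carry the visit date. The 48-month ideal window runs to day 1550, so 1550 − 1461 = 89 of its 181 days lie in the 60-month AE window. The 60-month ideal window has 89 of 181 days beyond that window. The share carried in equals the share carried out, so with similar attendance and yield the last window holds about one visit's worth of detections, as the 24-, 36- and 48-month windows do.

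**The case against.** The strongest reply is that the cut-off is deliberate. Day 1826 is exactly five years, the Protocol plans five years of follow-up, and the column heading marks these as absolute windows. An incidence for days 1462-1826 is not wrong because it leaves out events dated later. This stands as regards the rate. It does not settle the point, because the visible SAP collects later events without saying that they are excluded or where they are shown.

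A reader might infer from the 49% that about half of AEs first found at final visits are lost. The documents do not support that. Section 5.5.4 refers to onset and resolution dates when placing AEs in windows, so an AE found on day 1900 with onset on day 1800 is counted. A reader might also infer that five-year AE incidence is biased low; step 5 of the working shows why this does not follow.

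Nor is it established that reinterventions are affected. Section 5.5.7 does not say which column it uses, and if it uses the analysis window column there is no gap to day 2006. Its Kaplan-Meier analysis, over a period not tied to these windows, would in any case soften the effect. One could likewise read section 5.5.4 as meaning the analysis window column, but then the column labelled for AEs would have no evident use.

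Finally, the contents of SAP sections 7.1, 7.2 and 8.1 to 8.3 are not in the public text, so a listing or extra row for later events cannot be ruled out. The point is confined to what the visible SAP states.

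**Conclusion.** The point holds in a limited form. Under the visible SAP, AEs with onset on days 1827-2006 are collected but belong to no AE analysis window, and would be left out of the by-window AE tables for both zones. The gap is 180 days, 89 of them within the ideal 60-month visit window.

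The number of AEs affected is unknown. A plausible range for the share of AEs found at final visits runs from about 5-9% (onset uniform since the 48-month visit, visits spread evenly over the ideal or analysis window) to about half (onset dated to the visit). Because placement appears to be by onset date, the share is probably much nearer the lower end.

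The primary endpoints, which close at day 546 (Zone 2) and day 59 (Zone 0/1), are unaffected. The effect on reintervention incidence depends on a column that the SAP does not name.

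**What to change.** - Keep 1462-1826 as the five-year AE window. Add a separate AE row to Tables 3 and 4, and to the AE summaries, for onset after day 1826 through study completion. The uncovered days then fall from 180 to 0. Under the denominator rule in section 5.5.4, this row would use the subjects still in follow-up at its start.
- In section 5.5.7, name the window column used for site-reported reinterventions. If it is the AE column, add the same row.

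A separate row is better than a longer last window. A window of 1462-2006 would span 2006 − 1462 + 1 = 545 days against 365 now, and could not be compared with the earlier yearly windows. Extending only to day 1915 would leave 2006 − 1915 = 91 days uncovered.

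The cost is a small SAP wording change and minor programming; no new data are needed. The downside is a final row with short exposure that varies between subjects and is not comparable with the yearly windows, which a footnote should say.

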4.4 Data and Safety Monitoring Board

An independent Data and Safety Monitoring Board (DSMB) will review accumulating safety data on a regular basis and will advise the Sponsor regarding the continuing safety of study Subjects as well as the continuing validity and scientific merit of the study. The DSMB will be comprised of an interdisciplinary team of members with pertinent expertise in vascular or cardiothoracic surgery, as well as one biostatistician, who are not directly involved in the conduct of the study.

Based on the safety data, the DSMB will make recommendations to the Sponsor.

4.5 Clinical Events Committee

A Clinical Events Committee (CEC), consisting of appropriately trained Physicians with extensive relevant clinical experience, independent of the study, will adjudicate Primary Endpoint and Success Outcomes candidate events. The events to be adjudicated by CEC are detailed in **Appendix A**.

The CEC will also review Inclusion / Exclusion Deviations and adjudicate them as major or minor (see study protocol for these definitions).

4.6 Core Laboratory

All protocol required CTA imaging of the chest and/or chest, abdomen, and pelvis will be sent to the Core Lab via Medidata Medical Imaging (formerly known as Intelemage).

Analysis of pre-treatment and follow-up radiologic images will be conducted by an independent Core Lab (details in study protocol). At a minimum, the assessment will include:

- morphology of aortic lesion, adjacent aorta, and landing zones
- device status post-implant, including certain Success Outcomes as detailed in **Appendix A**.

5.0 Statistical Analyses

This section describes aspects of the statistical analysis which includes summarizing the analysis populations, analysis timing, and specifics on all planned analyses (Primary Endpoint analysis,

5.1 Analysis Populations

- 5.1.1 Primary Endpoint
 - 5.1.1.1 Zone 2 Aneurysm Cohort

The composite Primary Endpoint analysis population (to test the hypothesis) for the Zone 2 aneurysm cohort will be among enrolled Subjects (excluding those with a CEC adjudicated 'major' inclusion/exclusion criteria violation or FDA mandated exclusion) and is outlined as follows based on events described in **Section 2.3.1.1**:

- 1) Subjects with an event any time ≤ 546 days are a failure regardless of whether they had imaging in 12 month window
- Subjects that don't have imaging in the 12 month window and don't have an event ≤ 546 days are excluded
- Subjects with imaging in 12 month window and no event reported ≤ 546 days are successes
- 4) Subjects with >1 event just count once as failures

The rate (composite Primary Endpoint) within an analysis window (except for Procedure window) will use similar logic to that through 12 month window but will be window-dependent (i.e. 6 Month Primary Endpoint composite rate will be among those with an event in the 6 month window or had imaging in the 6 month window). All enrolled Subjects with no 'major' inclusion/exclusion criteria will be in the denominator in the Procedure window.

GORE CONFIDENTIAL INFORMATION

All hypothesis testing and Primary Analysis for the PMA will be based on Zone 2 Aneurysm Subjects accrued during the Primary Enrollment Period. Zone 2 Aneurysm Subjects accrued during Continued Access Enrollment will be analyzed separately for the PMA. Continued Access Enrollment Subjects may be pooled with the Primary Enrollment Subjects in subsequent reports and/or analysis.

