5.1.1.3 NAL Cohorts

[figure not shown]
No hypotheses will be tested for any of the NAL cohorts. An NAL cohort will be summarized separately if there are at least 10 Subjects for a cohort. Else, NAL Subjects may be grouped by Zone (Zone 0/1, Zone 2) for analysis instead.

The Primary Endpoint analysis population for each of the five NAL cohorts will be among all enrolled Subjects (excluding those with a CEC adjudicated 'major' inclusion/exclusion criteria violation or FDA mandated exclusion). In addition, the Primary Endpoint analysis population for each NAL cohort will follow Zonesimilar logic to that written for the two hypothesis-driven aneurysm test arms (as described above in Section 5.1.1.1 (Zone 2) and Section 5.1.1.2 (Zone 0/1)).

[figure not shown]

GORE CONFIDENTIAL INFORMATION

However, additional analysis may be done with different analysis population criteria.

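### The by-window composite rate admits event-free subjects only through imaging, but no CT or CTA is scheduled in the Post-Procedure window (days 1-14), so a composite tabulated there has no sensible denominator

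*SAP*

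**What the plan says.** **The rule (SAP 5.1.1.1, Zone 2 aneurysm cohort).** For the analysis through 12 months, "Subjects that don't have imaging in the 12 month window and don't have an event ≤ 546 days are excluded". The SAP then carries this over to single windows: "The rate (composite Primary Endpoint) within an analysis window (except for Procedure window) will use similar logic to that through 12 month window". Its example is that the "6 Month Primary Endpoint composite rate will be among those with an event in the 6 month window or had imaging in the 6 month" period. The one exempt window gets a full denominator: "All enrolled Subjects with no 'major' inclusion/exclusion criteria will be in the denominator in the Procedure window".

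**The windows (SAP 4.3, Table 3).** Procedure is day 0. The next row reads "Post-Procedure 1-14 1-14" for the ideal and analysis windows, and the 1 Month analysis window is days 15-59. The section adds that "any available data collected in the analysis windows will be summarized as occurring within the given window". Table 4 has the same post-procedure row for Zone 0/1.

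**The imaging schedule.** SAP Table 1 marks contrast CTA at Screening and then from 1 month, and non-contrast CT at 1 month. The Discharge column has neither. The completion angiogram belongs to the treatment day. In the Protocol's Zone 2 schedule, the Post Procedure list holds a physical examination and neurological scales. CTA appears under follow-up, with "Intervals: 1, 6, 12, 24, 36, 48, and 60 months post-treatment".

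**Reach.** SAP 5.1.1.3 says that "the Primary Endpoint analysis population for each NAL cohort will follow" logic similar to that of the aneurysm cohort in the same zone.

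**The concern.** An imaging condition makes sense where a scan is due: an event-free subject who missed the scan has not been fully assessed. In days 1-14 no scan is due. There the condition does not remove subjects who missed an assessment. It removes almost everyone without an event, while every subject with an event stays in.

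This differs from ordinary missed visits, because perfect adherence to the schedule would not repair the denominator. The scans that do occur are also unlikely to be a random sample. The one trigger for an extra scan that the Protocol names is suspected endoleak.

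At stake is a descriptive figure for the first two weeks after the procedure, when early reinterventions, strokes and spinal cord events would fall. A reader could take a rate of 40% or 100% as a safety signal when it is a product of the denominator rule.

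**Working it through.** The documents state no Post-Procedure composite rate, so there is no planned figure to reproduce. The check follows the rule as written.

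**Step 1: does the rule cover days 1-14?** SAP 5.1.1.1 covers every analysis window except Procedure. Table 3 gives Procedure (day 0) and Post-Procedure (days 1-14) separate rows and separate analysis windows. The exemption therefore does not extend to days 1-14.

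**Step 2: can an event-free subject qualify?** Only through imaging in days 1-14. Table 1 and the Protocol schedule none: the angiogram is on day 0, and the first follow-up CTA is at 1 month (ideal days 23-44, analysis days 15-59). Only an unscheduled scan qualifies.

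**Step 3: the resulting rate.** Let e = subjects with an event in days 1-14 and u = event-free subjects with an unscheduled scan in days 1-14.

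- Rule as written: failure rate = e / (e + u)
- All subjects at risk: failure rate = e / N, with N = 85 (Zone 2 Primary Enrollment, SAP 2.2), assuming no exclusions and nobody lost by day 1

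On scheduled imaging alone, u = 0. The rate is then e/e = 100% for any e of 1 or more, and 0/0 if e = 0.

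The documents give neither e nor u, so both are assumed below:

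| e | u | Rule as written | All 85 subjects |
|---|---|---|---|
| 3 | 0 | 3/3 = 100% | 3/85 = 3.5% |
| 3 | 4 | 3/7 = 43% | 3.5% |
| 3 | 8 | 3/11 = 27% | 3.5% |
| 3 | 20 | 3/23 = 13% | 3.5% |
| 5 | 0 | 5/5 = 100% | 5/85 = 5.9% |
| 5 | 5 | 5/10 = 50% | 5.9% |
| 5 | 20 | 5/25 = 20% | 5.9% |

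The two columns agree only when every event-free subject is scanned: for e = 3, u = 82 gives 3/85.

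**Step 4: is imaging needed to classify these subjects?** Mostly not. In the Appendix A rows available, the post-procedural failure components rest on site-reported events followed by adjudication. Only aortic rupture has an additional Core Lab route.

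**Step 5: what does the SAP do elsewhere?** The Procedure window uses all eligible enrolled subjects (5.1.1.1). Adverse events by window use subjects still in follow-up when the window opens (5.5.4). A denominator not based on imaging is therefore already in the plan.

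**The case against.** **No Post-Procedure composite output is named.** The SAP works through only the 6 Month window, and its list of tables is not in the available text. This stands, so the point is conditional on the row being tabulated. But the 1 Month analysis window opens at day 15. Without a Post-Procedure row, events in days 1-14 would enter no by-window composite rate. The SAP should settle the matter either way.

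**The rule asks only for similar logic.** True, but it names one exception and gives a concrete denominator. A programmer following it would apply the imaging condition to days 1-14. The dash for Post-Procedure in Table 3 is in the adverse event column; the composite's day-546 limit matches the analysis window column.

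**A reader might infer that the reported rate will be close to 100%.** The documents do not support that as a forecast. It is exact on scheduled imaging, but SAP 4.3 counts any available data in a window, and the number of unscheduled scans is unknown.

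**A reader might infer that early events would be visible only in this row, or that the non-aneurysm cohorts would have no other result.** Neither is so. SAP 5.5.4 reports adverse events by window among subjects in follow-up. Section 5.5.7 does the same for reinterventions and adds Kaplan-Meier estimates. Section 5.5.8 reports stroke and paraparesis/paraplegia among all subjects remaining in follow-up. The non-aneurysm cohorts receive these analyses (5.1.3) as well as the composite and component summaries (5.3.2).

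**The by-window sentence stands only in 5.1.1.1.** This is correct. Section 5.1.1.2 does not repeat it and refers to 5.1.1.1 only for the 12-month repeat. Extension to Zone 0/1 by-window rates is an inference.

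**Conclusion.** The point holds in conditional form. If a composite rate is tabulated for days 1-14 under SAP 5.1.1.1 as written, its denominator is not sensibly defined. The result is 100% or 0/0 on scheduled imaging, and otherwise a figure set by who happened to be scanned. With an assumed 3 events among 85 subjects it ranges from 100% (no unscheduled scans) through 43% (4 scans) to 27% (8 scans), against 3.5% of all subjects. The event and scan counts are illustrations.

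The effect is confined to a descriptive by-window rate. A reader might fear for the primary result, but the hypothesis tests use events through day 546 (Zone 2) and day 59 (Zone 0/1), and this rule does not touch them. It is worth correcting because the stated rule yields a misleading number and the correction costs very little.

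**What to change.** In SAP 5.1.1.1, extend the exemption in parentheses so that it names both the Procedure and the Post-Procedure windows. State that the Post-Procedure denominator is all analysis-population subjects still in follow-up at day 1. Alternatively, state that no composite rate is reported for the Post-Procedure window.

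Apply the same wording to the Zone 2 non-aneurysm cohorts, which inherit this logic through 5.1.1.3. Apply it to the Zone 0/1 cohorts if their by-window rates are meant to use it, and say in 5.1.1.2 whether they are.

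The cost is about one sentence in the SAP and a small change to the table program. No new data are needed, and the hypothesis tests and sample size do not change.
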